4. STATISTICAL ANALYSES

4.1. General Considerations

4.1.1. General Methodology

95% confidence levels will be used unless otherwise specified.

The exact confidence intervals around within-group proportions are derived using the method of Clopper and Pearson [[Clopper, 1934](#)].

Unless otherwise specified, continuous data will be summarized using descriptive statistics: n, mean, standard deviation (SD), median, minimum and maximum. Categorical data will be summarized as the number and percentage of participants in each category.

4.1.2. Baseline Definition

For all endpoints the baseline value will be the latest pre-dose assessment with a non-missing value.

Unless otherwise stated, if baseline data is missing, no derivation will be performed, and baseline will be set to missing.

4.2. Primary Endpoints Analyses

The primary immunogenicity analysis will be performed on the PPS and if more than 5% participants are eliminated from the PPS then a complementary analysis will be performed on ES.

4.2.1. Definition of endpoints

The VRR is defined as the percentage of participants who has at least:

- a 4-fold increase in the post last vaccination anti-gE antibody concentration as compared to the pre-vaccination anti-gE antibody concentration for participants who are seropositive at baseline.
OR
- a 4-fold increase in the post last vaccination anti-gE antibody concentration as compared to the anti-gE antibody cut-off value (97 mIU/ml) for seropositivity for participants who are seronegative at baseline.

Two-sided 95% CIs for VRR will be computed by Clopper-Pearson method [[Clopper, 1934](#)].

4.2.2. Main analytical approach

The point estimate and the 95% CI for VRR on anti-gE antibody concentration as assessed by ELISA will be calculated in all participants at 1-month post-dose 2 (Month 3).

As stated in Section 2 the objective is met if the LL of the 95% CI of the VRR for anti-gE antibody concentration 1 month after the second HZ/su dose is at least 60%.

4.3. Secondary Endpoints Analyses

4.3.1. Key/Confirmatory secondary endpoints

4.3.1.1. Confirmatory secondary immunogenicity endpoints

The secondary confirmatory immunogenicity analysis will be performed on the PPS and if more than 5% participants are eliminated from the PPS then a complementary analysis will be performed on ES.

4.3.1.2. Definition of endpoints

The geometric mean concentration (GMC) calculations are performed by taking the anti-log of the mean of the log base 10 concentration transformations. For descriptive statistics only, antibody concentrations below the cut-off of the assay will be imputed with a value equal to half the cut-off for the purpose of GMC calculation.

4.3.1.3. Main analytical approach

For the secondary confirmatory group comparison, the GMC ratio with nominal 95% CI will also be provided. This will be obtained using an analysis of variance (ANOVA) model on log-transformed concentrations adjusted for age-strata (50-69 YOA and ≥ 70 YOA) and baseline titres as continuous covariate and will use Satterthwaite method for adjusting the degree of freedom for unequal variance.

For this analysis, the following SAS code using the proc mixed procedure will be used to do the model fitting:

```
PROC MIXED DATA=sero;
  CLASS grp_labl agecat; /*age-minimization factor*/
  MODEL log_val=grp_labl agecat base/DDFM=satterth;
  REPEATES/GROUP=grp_labl;
  LSMEANS grp_labl /AT MEANS CL DIFF ALPHA=0.05 COV;
  ODS OUTPUT LSMEANS=m_lsml;
  ODS OUTPUT DIFFS=m_difl;
  RUN;
```

The group GMC ratio will be based on a back transformation of group contrast in an ANCOVA model applied to the logarithm-transformed concentrations.

4.3.2. Key secondary immunogenicity endpoint

Descriptive statistics of immune response with respect to anti-gE assessed by ELISA at each timepoint and by study group will be presented:

- Number and percentage of participants with anti-gE assessed by ELISA above seropositivity cut-off will be tabulated with 95% CI.
- GMCs will be tabulated with 95% CI.
- Geometric mean of ratios of antibody concentrations at 1- month post-dose 2 timepoint over pre-study intervention administration (MGI) will be tabulated with 95% CI.

4.3.3. Key secondary safety endpoints

The analyses for safety will be descriptive and based on the ES. The analyses will be performed by study group.

The results for the analysis of safety and reactogenicity will be tabulated as follows:

- Solicited administration site AEs and solicited systemic AEs
 - Number and percentage of participants reporting each solicited administration site AE (any grade, grade 3, resulting in a medically-attended visit) during the 7-day follow-up period after each dose and overall per participant and per dose will be tabulated with exact 95% CIs.
 - Number and percentage of participants reporting each solicited systemic AE (any grade, grade 3, resulting in a medically-attended visit) during the 7-day follow-up period after each dose and overall per participant and per dose will be tabulated with exact 95% CIs.
- Unsolicited AEs: Number and percentage of participants reporting unsolicited AE (any grade, grade 3, any related, grade 3 related, resulting in a medically-attended visit) within 30 days after any dose coded by the Medical Dictionary for Regulatory Activities (MedDRA) by primary system organ class (SOC) and preferred term (PT) with exact 95% CIs will be tabulated.
- SAEs and pIMDs: Number and percentage of participants reporting SAEs (any and related), fatal SAEs (any and related) and pIMDs (any and related) from Dose 1 (Day 1) up to 30 days post last dose and from Dose 1 (Day 1) up to study end coded by the MedDRA primary SOC and PT with exact 95% CIs will be tabulated.
- Listing of fatal SAEs, SAEs, pIMDs and withdrawals (from the study or from vaccination) due to AEs, SAEs, solicited and unsolicited AEs will be generated from first study intervention up to study end.
- Listing of pregnancy during the entire study period will be generated.

4.3.4. Supportive secondary endpoints

Not applicable

4.4. Tertiary/Exploratory Endpoints Analyses

Not Applicable.

4.5. Other Safety Analyses

Below are the other safety analyses planned for the final analysis and based on the ES. These analyses will be performed by study group.

- The percentage of participants with at least 1 administrative site adverse event (solicited only), with at least one systemic AE (solicited only) and with any AE (solicited only), all with onset during the solicited 7-day follow-up period, will be tabulated with exact 95% CI after each vaccine dose and overall. The same tabulations will be done for grade 3 solicited AEs.
- In the solicited systemic adverse event table, fever will be reported per 0.5°C cumulative increments.
- Duration of each solicited administrative site and systemic AE during the solicited follow-up period will be presented. Total duration of each individual solicited administrative site and systemic AE will be tabulated.
- Duration of each grade 3 solicited administrative site and systemic AE during the solicited follow-up period will be presented. Total duration of each individual solicited grade 3 administrative site and systemic AE will be tabulated.

4.5.1. COVID-19 Assessment and COVID-19 AEs

A standardized MedDRA Query (SMQ) will be used to identify all COVID-19 AEs.

The overall incidence of AEs and SAEs of COVID-19, COVID-19 AEs leading to study intervention discontinuation, COVID-19 AEs leading to study withdrawal, and severe COVID-19 AEs will be summarized. The incidence of these events at individual PT level can be obtained from the standard AE/SAE summaries.

COVID-19 assessments (confirmed, probable and suspected diagnosis) for participants with COVID-19 AEs will be summarized.

The number and percentages of participants with concomitant vaccination (COVID-19) before and during the study will be tabulated with exact 95% CI.

Summaries of the number of participants who had a COVID-19 diagnosis test performed and the number of participants with positive, negative, or indeterminate results will be presented.

Additional tables may be planned as required.

4.6. Other Analyses

Not applicable.

4.7. Interim Analyses

No interim analysis is planned for this study. An EoS analysis with all data including the safety data obtained until study end (6 months post-dose 2) will be performed. A Clinical Study Report (CSR) containing all available data will be written and made available to the investigators. Individual listings will only be provided at this stage.

4.7.1. Blinded Early Safety Report

To fulfil the post-approval commitment to the Indian regulatory authority, a blinded early safety assessment report after completion of 30 days safety follow-up post HZ/su dose 2 (i.e., Visit 3, Month 3) for the initial 200 randomised participants will be provided and the following analyses will be performed. The analyses performed will be descriptive in nature.

1. Table on summary of participants withdrawn up to the snapshot date with reasons for withdrawal on the Exposed Set
2. Summary of demography and baseline characteristics on the Exposed Set
3. Table showing the exposure to study intervention on the Enrolled Set
4. Number and percentage of participants with any, grade 3, or medically attended solicited administration site events, per dose, in the Exposed Set.
5. *Number and percentage of participants with any, grade 3, or medically attended solicited systemic events, per dose, in the Exposed Set*
6. Number and percentage of participants with any, grade 3, related, or grade 3 related unsolicited adverse events with onset within 30 days following any dose in the Exposed Set
7. Number and percentage of participants with serious adverse events from first dose up to 30 days post last dose in the Exposed Set
8. Number and percentage of participants with serious adverse events from first dose up to snapshot day in the Exposed Set
9. Number and percentage of participants with pIMDs from first dose up to 30 days post last dose in the Exposed Set
10. Number and percentage of participants with pIMDs from first dose up to snapshot day in the Exposed Set
11. Listing of SAEs from first dose up to snapshot day.
12. Listing of pIMDs from first dose up to snapshot day.

All the data derivation rules for demography and safety analyses of [Appendix 2](#) will be applicable for the above demography and safety analyses.

4.8. Changes to Protocol Defined Analyses

Not applicable.

5. SAMPLE SIZE DETERMINATION

Approximately 288 (144 participants per study group) eligible participants will be randomised to achieve 200 (100 participants per study group) evaluable participants for the evaluation of the primary objective assuming that approximately 30% of the enrolled participants will not be evaluable. Participants who withdraw from the study will not be replaced.

Considering a 95% VRR in the HZ/su group, the study has at least 99% power to meet the primary objective under the hypothesis given below:-

- Null hypothesis: The VRR for anti-gE ELISA at 1 month after second HZ/su dose in participants from India is less than 60%.
- Alternative hypothesis: The VRR for anti-gE ELISA at 1 month after second HZ/su dose in participants from India is at least 60%.

Power to show the LL of the 95% CI for VRR at one month after second HZ/su dose.

Endpoint	NI criteria	N1:N2 (evaluable)	Reference**	Power*
Vaccine response rate – anti-gE ELISA	LL of 95% CI for VRR $\geq 60\%$	100:100	95%	$\geq 99\%$

*Power computed using PASS 2019 software, Non-Inferiority Test for one proportion, 1-sided alpha=2.5%;

**References used for the sample size calculation: ZOSTER-006 study.

Considering the adjusted GMC ratio of 44.31 between HZ/su and Placebo group and SD of 0.30 and 0.46 for HZ/su and Placebo group, respectively, the study has at least 99% power to meet the secondary confirmatory objective under below hypothesis.

- Null hypothesis: The adjusted GMC ratio for anti-gE ELISA at 1 month after second study intervention dose in participants from India is less than 3.
- Alternative hypothesis: The adjusted GMC ratio for anti-gE ELISA at 1 month after second study intervention dose in participants from India is greater than or equal to 3.

Power to show the LL of the 95% CI for adjusted GMC ratio at one month after second dose.

Endpoint	Criteria for evaluation	N1:N2 (evaluable)	Reference**	Power*
Adjusted GMC ratio	LL of 95% CI for adjusted GMC ratio ≥ 3	100:100	Adjusted GMC ratio – 44.31 SD for HZ/su group – 0.30 SD for Placebo group – 0.46	$\geq 99\%$

*Power computed using PASS 2019 software, Two-Sample T-Tests for Superiority by a Margin Allowing Unequal Variance,

1-sided alpha=2.5%;

**References used for the sample size calculation: ZOSTER-006 study.

6. SUPPORTING DOCUMENTATION

6.1. Appendix 1 Study Population Analyses

6.1.1. Participant Disposition

A summary of the number and percentage of participants who completed the study as well as those who withdrew from the study will be provided. Reasons for study withdrawal will be summarized. For those who neither completed nor withdrawn, they will be categorized as on study intervention or in follow up. This analysis will be based on the ES.

The number of participants enrolled into the study as well as the number of participants excluded from the PPS analyses will be presented through 2 consort tables:

- Consort table 1: Showing the participants disposition from *participants with ICF signed to Enrolled Set and from Enrolled Set* to ES.
- Consort table 2: Showing the participants disposition for ES to PPS.

6.1.2. Demographic and Baseline Characteristics

Demographic and other baseline characteristics will be described for the ES and the PPS

Demographic characteristics (age at first vaccination with study intervention in years, age category [50-69, ≥ 70 YOA], sex, race and ethnicity) will be summarized using descriptive statistics:

- Frequency tables will be generated for categorical variables such as center.
- Mean, standard deviation, median, minimum and maximum will be provided for continuous data such as age.

Number of participants by center will be presented on ES. Percentage of Enrolled participants by age categories (18-64, 65-84, ≥ 85) YOA will be tabulated by group for the purpose of web disclosure.

6.1.3. Protocol Deviations

The number of participants enrolled into the study as well as the number of participants excluded from the per protocol set (PPS) analyses will be tabulated for the total population.

The number of participants enrolled into the study as well as the number of participants excluded from the ES will be tabulated for the total population. This will be based on all enrolled participants.

Important protocol deviations will be summarized. Protocol deviations which result in exclusion from an analysis set will also be summarized. Data will be reviewed prior to unblinding and freezing the database to ensure all deviations leading to analysis population exclusions are captured and categorised in the protocol deviations ADaM dataset.

6.1.4. Prior and Concomitant Medications

No table is planned for the prior medications taken by participants.

The proportion of participants with concomitant medications (any medication, any antipyretic and any antipyretic taken prophylactically, respectively) will be tabulated, within 30 days post each vaccination (i.e., on the day of vaccination and 29 subsequent days) with study intervention and overall, with exact 95% CI.

6.1.5. Prior and Concomitant Vaccinations

No table is planned for the prior vaccinations taken by participants.

The proportion of participants with concomitant vaccinations will be tabulated, within 30 days post each vaccination (i.e., on the day of vaccination and 29 subsequent days) with study intervention and overall, with exact 95% CI.

6.1.6. Study Intervention Compliance

The number of doses administered will be tabulated.

The number and percentage of participants who returned the diary cards and those who returned the diary cards with documentation of the presence or absence of AEs will be tabulated on the Exposed Set.

Summary of time interval between Visit 1 or 2 and Visit 2 and Visit 3 will be tabulated for the Exposed Set.

6.1.7. Additional Analyses Due to the COVID-19 Pandemic

Depending on how the COVID-19 pandemic evolves, the SAP may be amended to reflect the additional analyses corresponding to COVID-19.

6.2. Appendix 2 Data Derivations Rule

This section contains standard rules for data display and derivation for clinical and epidemiological studies.

6.2.1. Attributing events to vaccine doses

The dose relative to an event is the most recent study intervention dose given to a participant prior to the start of a given event. For example, if the start date of an adverse event is between Dose 1 and Dose 2, the relative dose will be Dose 1.

If an event starts on the same day as a study dose, the relative dose will be derived from the additional information provided in the case report form (CRF) using the contents of the flag indicating if the event occurred before or after study dose. If ‘after study dose’ is selected, the relative dose for the event will be the one administered on the start day of the event. If ‘before study dose’ is selected, the relative dose for the event will be the dose prior to this one.

6.2.2. Handling of missing data

6.2.2.1. Dates

When partially completed dates (i.e. dates missing a day and/or month) are used in calculations, the following standard rules will be applied:

- A missing day will be replaced by 15
- A missing day and month will be replaced by June 30th.

The following exceptions apply:

When partially completed dates (i.e. with missing day or month) are used in calculations, the following rules will be applied:

- Adverse event start dates with missing day:
 - If the month is not the same as the study intervention dose, then the imputed start date will be the 1st of the month
 - If the event starts in the same month as at least one of the study interventions, the flag indicating if the event occurred before or after study intervention (AE.AESTRTPT) will be used to complete the date. If ‘after vaccination’ is selected, the imputed start date will match the study intervention dose given during that month. If ‘before vaccination’ is selected, the imputed date will be one day before the study intervention dose given during that month.
 - If we cannot impute the missing parts of the date using the rule under above categories, then we need to apply Version 15 rule - 15 for the missing day and 30JUN for missing month and day.

- Adverse event start dates with missing day and month:
 - If the year is not the same as the vaccine dose, then the imputed start date will be the 1st of January.
 - If the event starts in the same year as the vaccine dose, the flag indicating if the event occurred before or after vaccination (AE.AESTRTPT) will be used to complete the date. If ‘after vaccination’ is selected, the imputed start date will match the first study intervention dose given during that year. If ‘before vaccination’ is selected, the imputed date will be one day before the first study intervention dose given during that year.
 - If we cannot impute the missing parts of the date using the rule under above categories, then we need to apply Version 15 rule - 15 for the missing day and 30JUN for missing month and day.
- Adverse event end dates with missing day: the imputed end date will be the last day of the month (30 or 31) or the study conclusion date whichever comes first.
- Adverse event end dates with missing day and month: the imputed end date will be the last day of the year (31st of December) or the study conclusion date whichever comes first.

All incomplete concomitant medication/vaccination start/end date will follow the rules above.

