#### **10.3.8.1. Time period for collecting and recording AEs, SAEs, pIMDs and pregnancies**

All AEs that occur during 30 days following administration of each dose of study intervention (Day 1 to Day 30) must be recorded into the appropriate section of the eCRF, irrespective of their intensity or whether or not they are considered related to the study intervention.

The time period for collecting and recording all SAEs will begin at the first receipt of study vaccine and will end 6 months following administration of the last dose of study vaccine for each participant. See Section [10.3.10](#) for instructions on reporting of SAEs.

All AEs/SAEs leading to withdrawal from the study will be collected and recorded from the time of the first receipt of study vaccine.

SAEs that are related to the study vaccine will be collected and recorded from the time of the first receipt of study vaccine until the participant is discharged from the study.

In addition to the above-mentioned reporting requirements and in order to fulfil international reporting obligations, SAEs that are related to study participation (i.e. protocol-mandated procedures, invasive tests, a change from existing therapy) or are related to a concurrent GlaxoSmithKline medication/vaccine will be collected and recorded from the time the participant consents to participate in the study until she/he is discharged from the study.

The time period for collecting and recording pregnancies will begin at the first receipt of study vaccine until study end. See Section [8.3](#) for instructions on reporting of pregnancies. This applies to pregnancy cases with exposure to the study intervention at any age of gestation. The timing of exposure to the study intervention during pregnancy is estimated in relation to the first day of the last menstrual period, ultrasound or known date of fertilisation (e.g. assisted reproductive technology).

The time period for collecting and recording of pIMDs will begin at the first receipt of study vaccine and will end 6 months following administration of the last dose of study vaccine. See Section [8.3](#) for instructions on reporting of pIMDs.

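### The last-resort rule for partial adverse-event start dates (15th of the month, or 30 June) ignores dose dates and can misplace post-dose events, including before Dose 1

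*SAP*

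**What the plan says.** SAP 6.2.2.1 (Dates) sets three tiers for an adverse-event start date with the day missing.

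1. No dose in the known month: "If the month is not the same as the study intervention dose, then the imputed start date will be the 1st of the month".
2. A dose in the known month: "the flag indicating if the event occurred before or after study intervention (AE.AESTRTPT) will be used to complete the date". If the flag says *after*, "the imputed start date will match the study intervention dose given during that month"; if it says *before*, the date is one day earlier than the dose.
3. "If we cannot impute the missing parts of the date using the rule under above categories", then "apply Version 15 rule - 15 for the missing day and 30JUN for missing month and day".

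With day and month both missing, the tiers are parallel. The date is 1 January if the year contains no dose. Otherwise the flag is used, and for *after* "the imputed start date will match the first study intervention dose given during that year". The same fallback follows.

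SAP 6.2.1 and 6.2.3.5 derive the relative dose and the onset day from the start date. SAP 4.3.3 tabulates unsolicited AEs within 30 days after any dose, and SAEs and pIMDs "from Dose 1 (Day 1) up to 30 days post last dose and from Dose 1 (Day 1) up to study end". Protocol 10.3.8.1 states: "The time period for collecting and recording all SAEs will begin at the first receipt of study vaccine". It sets the same starting point for pIMDs. SAEs related to study participation or to a concurrent sponsor product are collected from consent.

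**The concern.** Tier 1 already covers every month or year without a dose. Tier 3 is therefore reached, in practice, only when the known month or year contains a dose and the flag is missing. In that situation the position of the date relative to the dose decides whether the event is tabulated, yet tier 3 takes no account of the dose date. I found no rule in the SAP that moves an imputed date up to Dose 1, treats a missing flag as *after*, or keeps such an event in the tables.

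What is lost depends on where the date lands:

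- **Before Dose 1.** The event leaves the 30-day unsolicited table. An SAE or pIMD also leaves both tables that start at Dose 1. Most events are collected only from Dose 1, so such a date is inconsistent with how the event came to be recorded.
- **Between the doses, outside Days 1–30.** The event leaves the 30-day unsolicited table and is attributed to the wrong dose if it followed Dose 2. An SAE or pIMD stays in both from-Dose-1 tables.
- **More than 30 days after the last dose (30 June branch).** The event leaves the 30-day unsolicited table. An SAE or pIMD stays in the table to study end but leaves the one that stops 30 days after the last dose.

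SAP 4.7.1 applies the same derivation rules to the blinded early safety report.

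**Working it through.** The plan gives no figure to reproduce, so the rule was enumerated by calendar.

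**Inputs from the documents.** Fallback dates of the 15th and 30 June (SAP 6.2.2.1); a window of Days 1–30 with the dose day as Day 1 (Protocol 10.3.8, SAP 6.2.3.5); a dose interval of 60 days planned and 49–83 allowed (SAP 3.1, Table 2).

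**Assumptions.** Dose 1 is equally likely on each date of a 365-day year, true onset is uniform over Days 1–30, and the flag is missing. An imputed date that equals a dose date is counted as post-dose, which favours the plan.

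**Examples (60-day interval)**

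| Dose 1 | Dose 2 | True onset | Imputed | Result |
|---|---|---|---|---|
| 20 Mar | 19 May | 24 Mar (Dose 1, Day 5) | 15 Mar | before Dose 1 |
| 21 Mar | 20 May | 24 May (Dose 2, Day 5) | 15 May | Dose 1, Day 56 |
| 10 Jul | 8 Sep | 14 Jul (Dose 1, Day 5) | 30 Jun | before Dose 1 |
| 10 Feb | 11 Apr | 14 Apr (Dose 2, Day 4) | 30 Jun | Dose 2, Day 81 |

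**Day missing.** Take a dose on day *d* of a month with *L* days.

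- If *d* ≤ 15, the imputed onset is Day 16 − *d*, between 1 and 15, so it is in the window.
- If *d* ≥ 16 (185 of 365 dates, 51%), the imputed date precedes the dose. For Dose 2 it lies at most 16 days before the dose, so at the minimum interval it is Day 49 − 16 + 1 = 34 of Dose 1 or later, always outside the window.
- In-window onsets in the dose month number Σ min(30, *L* − *d* + 1) over *d* = 1 to *L*: 495, 465 and 406 for months of 31, 30 and 28 days.
- Those lost number (*L* − 15)(*L* − 14)/2: 136, 120 and 91.
- Year total in window: 7×495 + 4×465 + 406 = 5,731. Lost: 7×136 + 4×120 + 91 = 1,523. Share lost: 1,523/5,731 = **26.6%** for either dose at 60 or 83 days. For Dose 1 events all of this is placement before Dose 1.
- At 49 days, another 6,449 − 5,731 = 718 Dose 1 onsets fall in the month of Dose 2 but not of Dose 1. All are moved out of the window. Pooled loss: (1,523 + 718 + 1,523)/(6,449 + 5,731) = **30.9%**.

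**Day and month missing (60-day interval)**

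| True event after | Before Dose 1 | After Dose 1, out of window | In window |
|---|---|---|---|
| Dose 1 | 46.4% | 37.1% | 16.4% |
| Dose 2 | 31.2% | 51.6% | 17.1% |

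With the two doses weighted equally, (46.4 + 31.2)/2 = **38.8%** fall before Dose 1, and 100 − (16.4 + 17.1)/2 = **83%** fall outside any 30-day window. The 83% includes the 38.8%.

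**The opposite error.** With Dose 2 on the 10th and true onset on the 5th, the imputed date is the 15th, Day 6 of Dose 2. For onsets in the dose month during the 30 days before a dose, none truly in a window at a 60-day interval, the total is Σ(*d* − 1): 465, 435 and 378 by month length, or 7×465 + 4×435 + 378 = 5,373 over the year. Those with *d* ≤ 15 are moved into the window: 105 per month, 1,260 per year. Share: 1,260/5,373 = **23.5%**.

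**The case against.** Three arguments deserve weight.

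**The rule is rarely reached.** It needs a partial date, a dose in the same month or year, and no flag. Diaries cover the dose day and the next 29 days and come back at the next visit. SAEs and pIMDs go on expedited reports within 24 hours, and monitors verify source data. This stands. The documents give no count, and a missing day together with a missing flag is least plausible for SAEs and pIMDs.

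**The direction is not fixed.** A reader might infer that the rule only ever removes events and so biases safety percentages downward. The documents do not support that. Day 15 also brings events into the window, as the 23.5% shows, and pre-dose onsets do exist in this plan: the *before* branch provides for them, Protocol 10.3.1.1 admits pre-intervention events from protocol procedures, and some SAEs are collected from consent. What remains is narrower: placement before Dose 1 can only remove post-dose events, and for most recorded events it is inconsistent with the collection rules.

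**Imputing the dose date is itself a convention.** It will count some true pre-dose events as post-dose, and using the first dose of the year attributes a Dose 2 event to Dose 1. Both points are fair. The SAP already accepts the second in its *after* rule, and the first errs on the conservative side for safety.

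**Conclusion.** The point holds as a minor one. The fallback is a stated rule, not missing detail, and nothing else in the SAP corrects its result.

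The shares are about 27% lost with the day missing (31% at a 49-day interval), and about 39% before Dose 1 and 83% out of window with day and month missing. All are conditional on the fallback being reached and rest on uniform dose and onset dates. They are not shares of all adverse events. Nor should the 27% be read as the share of SAEs and pIMDs lost: a Dose 2 SAE or pIMD redated between the doses stays in the from-Dose-1 tables.

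The number of affected records is unknown and probably small. Safety is descriptive and no confirmatory analysis is touched. The reason to act is that SAEs and pIMDs are likely to be few among 144 participants per group, so one misdated event can change a table.

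**What to change.** In SAP 6.2.2.1, replace the fallback in both adverse-event start-date lists with a rule to this effect:

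- If the flag is missing and the known month contains a dose, impute that dose date. If only the year is known, impute the first dose of that year, as the existing *after* rule does. Count the event as starting after that dose, because SAP 6.2.1 otherwise turns to the same missing flag for same-day events.
- Make an exception when a known end date is earlier than that dose; the imputed start must then be no later than the end date.
- Do not impute a date before Dose 1 for any unsolicited AE, SAE or pIMD, except pre-dose events collected from consent: SAEs related to study participation or to a concurrent sponsor product, and events caused by protocol procedures.
- Keep the 15th and 30 June for other dates.

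Where no exception applies, every imputed date falls on a dose date (onset Day 1), so no true post-dose event is placed before Dose 1 or outside the 30-day window. The cost is a sentence or two and a small programming change. The downside is that an occasional true pre-dose event is counted as post-dose.
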